6.3 Dose Modification

One level dose reduction per the dose escalation scheme, for toxicity is allowed. If the toxicity is equivalent to a DLT (see Section 6.1.2) then continued treatment at a lower dose level needs approval by the sponsor and/or SRC.

6.4 Concomitant Treatment

Patients must not receive any other concurrent anti-cancer therapy, including investigational agents while on study treatment.

Unexpected serious adverse reactions, including severe allergic reactions, may be treated according to standard-of-care and institutional practice without limitations, including antihistamines, corticosteroids, cytokine antagonists, antipyretics and analgesics.

Supportive treatment may include anti-emetic, anti-diarrheal, anti-pyretic, anti-histamines, analgesics, antibiotics, and blood products. At the discretion of the treating physician, patients may receive anti-histamine prophylaxis according to the standard of care in clinical practice.

Local and/or systemic injection reactions may be treated with antihistamines, antipyretics, and/or analgesics in accordance with standard local practice and Investigator's clinical judgment.

For patients with bone metastases requiring medication for treatment and/or prevention of skeletal-related events bisphosphonates are permissible but RANK-ligand inhibitors are prohibited throughout the trial.

While on treatment in the study, use of the type of medications specified below should be avoided. HS-130 and HS-110 will be temporarily stopped for the period of time these medications are used.

- Immunosuppressive agents, except to treat a drug-related adverse event
- Systemic corticosteroids > 10 mg daily prednisone equivalent

Ocular, intra-articular, intranasal, and inhalational corticosteroids are allowed.

6.5 Monitoring Subject Compliance

This study will be monitored by Heat Biologics or its CRO according to ICH E6 guidelines of GCP. The study site monitor will regularly visit the study sites to ensure that the study is conducted according to the protocol and GCP principles.

7.0 STUDY EVALUATIONS

7.1 Schedule of Study Evaluations

Study evaluations are summarized in [Table 3](#) and described in Sections [1.1](#) through [7.6](#).

Table 3: Schedule of Assessments

	Pre-treatment	Cycle 1 (± 2 days) ^p		Cycle 2 (± 2 days) ^p		Cycle 3 and beyond (± 2 days) ^p	30-day safety follow up visit (±3 days) ^m	Post-treatment Follow-up (±1 week) ⁿ	Survival Follow-up (±2 week) ^o	
		Day 1	Day 8	Day 1	Day 8	Day 1				
Informed consent	X ^a									
Medical history	X ^a									
Physical exam	X ^b	X ^b	X	X	X	X	X			
Weight	X ^b	X ^b	X	X	X	X	X			
Vital signs ^c	X ^b	X	X	X	X	X	X			
ECG ^d	X ^a	X		X		X	X			
ECOG performance status	X ^b	X ^b	X	X	X	X	X			
Tumor measurement ^e	X ^a					X ^e		X ⁿ		
Hematology ^f	X ^b	X ^b		X		X	X			
Blood chemistry ^g	X ^b	X ^b		X		X	X			
Pregnancy test ^h	X ^b									
Blood Sample for Immune Response Labs ⁱ		X ⁱ	X ⁱ	X ⁱ	X ⁱ		X			
Blood sample for cytokines/chemokines ^j		X ⁱ		X ⁱ		X ⁱ				
Biopsy ^k	X ^a					X ^k				
HS-130 and HS-110 administration ^l		X		X		X				
Concomitant medications/Treatment	X ^a	←..... Throughout Study→						X	X	X ^o
Adverse events		←..... Throughout Study→						X	X	
Survival Status									X ^o	

- a: Within 28 days prior to treatment.
- b: Within 7 days prior to treatment. For Cycle 1 Day 1, these tests may be performed within 3 days. Tests done within 3 days of Cycle 1 Day 1 do not need to be repeated unless clinically indicated.
- c: Vital signs, including blood pressure, heart rate, respiratory rate, and temperature. During Cycle 1 and Cycle 2 on Day 1: Before HS130/HS110 treatment; after treatment at 30 mins (± 5 min), 1hr (± 5 min). Other Cycles on Day 1: only Pre-dose.
- d: Standard 12-lead ECG (in triplicate) while patient is in semi-recumbent position pre-dose on Day 1 of each cycle.
- e: Tumor measurement per RECIST 1.1¹. Patients will be evaluated at screening and then after every 8-weeks ± 1 week from C1D1 until disease progression.
- f: Hematology, including hemoglobin, WBC with differential, and platelet count (Approximately 5 mL blood per draw).
- g: Blood chemistry, including sodium, potassium, BUN, glucose, SGOT/SGPT (ALT/AST), alkaline phosphatase, total protein, total bilirubin, albumin, lactate dehydrogenase (LDH), TSH, creatinine, C-reactive protein and calcium. (Approximately 5 mL blood per draw).
- h: Pregnancy test; for women of childbearing potential, a negative pregnancy test (urine or serum) must be documented.
- i: Approximately 23 mL blood per draw Day 1 (pre-dose) and Day 8 for C1 and C2, and at 30-day safety follow-up visit for immune response labs (See Section 8.6).
- j: Cytokines and chemokines sample collection on Day 1 for C1 and C2 at time-points: Before HS130/HS110 treatment, and 2 hr ± 10 minutes after treatment. For C3 and beyond only if the patient is symptomatic i.e. flu-like symptoms, fever, or allergic reactions. (Approximately 3 mL blood per draw).
- k: Pre-treatment biopsy (archival tissue may be submitted if collected less than 6-months prior to C1D1 and the local pathologist confirms that an adequate amount of tissue/tumor cells exist to allow completion of all testing as outlined in the Specimen Collection Manual) and on-treatment biopsy collected within 5-14 days after patient completes 2nd dose of HS-130/HS-110 for genomic and proteomic analysis of exploratory biomarkers (e.g. mIHC). Biopsy should be collected for patients with accessible tumor lesions, incl. metastases (e.g. lymph node metastases) where it is considered feasible without a risk of complications for the patient. Coagulation parameters and blood cells should be assessed and reviewed per institutional standard prior to any biopsy.
- l: HS-130 and HS-110 will be administered via intradermal injections/re-injections (up to 10 total) on Day 1 of each cycle, depending on the assigned dose level. (See section 6.1 Drug preparation and administration)
- m: All assessments should be performed at 30 days ± 3 days after the last treatment, during the 30-day safety follow-up visit.
- n: If a patient stops treatment for any other reason than progressive disease, radiological assessments will continue every 12 weeks starting from the date of patient's last dose until disease progression or initiation of new anti-cancer treatment.
- o: Survival status and subsequent anti-cancer therapy information will be collected approximately every 12 weeks in a clinic visit, or by telephone from the time of disease progression or initiation of new anti-cancer treatment until death.
- p: Each cycle is 14 days.

7.2 Pre-treatment

Within 28 days from C1D1:

- Sign informed consent
- ECG in triplicate (a standard 12-lead ECG is taken while patient is in a semi-recumbent position)
- Medical history including prior treatments and surgeries, prior medications, and pre-existing clinical signs and symptoms
- Imaging for tumor measurements by RECIST 1.1¹
- Fresh Biopsy (archival tissue may be submitted if collected less than 6-months prior to C1D1 and the local pathologist confirms that an adequate amount of tissue/tumor cells exist to allow completion of all testing as outlined in the Tumor Biopsy Collection Manual). Note that coagulation tests should be reviewed prior to procedure per institutional standards.

Within 7 days from C1D1:

- Physical exam
- Weight
- Vital signs (blood pressure, heart rate, respiratory rate, and temperature)
- ECOG performance status ([APPENDIX I](#))
- Pregnancy test for women of childbearing potential (i.e. not surgically sterile or post-menopausal > 1 year)
- Blood draw for Hematology, Blood chemistry

7.3 During Treatment

Each cycle will be 14-days.

7.3.1 Cycle 1

7.3.1.1 Cycle 1 Day 1 ± 2 days (Week 1)

- Physical Exam (may be done within 3 days prior)
- Weight (may be done within 3 days prior)
- Vital signs (blood pressure, heart rate, respiratory rate, and temperature: Before HS130/HS110 treatment; after HS130/HS110 treatment at 30 mins (±5m), and 1hr (±5m))
- ECG in triplicate (a standard 12-lead ECG is taken while patient is in a semi-recumbent position; pre-dose)
- ECOG performance status (may be done within 3 days prior) ([APPENDIX I](#))
- Blood draw for Hematology (may be done within 3 days prior)
- Blood draw for Blood chemistry tests (may be done within 3 days prior)
- HS-130/HS-110 administration
- Blood draw for immune response labs (Immunological Effect/Immune re-activation) (Pre-dose)
- Blood draw for Cytokines/Chemokines (Pre-dose, and 2 hr ± 10 minutes after completion of HS130/HS110 treatment)
- Record Concomitant medications (Update prior medications if applicable)
- Record Adverse events

7.3.1.2 Cycle 1 Day 8 ± 2 days (Week 2)

- Physical Exam

- Weight
- Vital signs (blood pressure, heart rate, respiratory rate, and temperature)
- ECOG Performance status ([APPENDIX I](#))
- Blood draw for immune response labs (Immunological Effect/Immune re-activation)
- Record Concomitant medications
- Record Adverse events

7.3.2 Cycle 2

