The first cohort will employ an accelerated design to evaluate the first 4 dose levels in single patients. There will be a staggered enrollment with a minimum 1-week delay between each patient in cohort 1. If any drug-related \geq Grade 2 (other than Grade 2 injection site reaction with pain) event occurs during the first cycle of treatment, the study will revert to 3+3 design starting at that dose level.

Subsequent cohorts in the dose escalation phase will enroll patients following the standard 3+3 design. Three patients will be enrolled in each subsequent dose cohort and enrolled with a (minimum) 1-week staggered delay (i.e. Patient 2 to be dosed \geq 1-week after Patient 1 received the first dose, and Patient 3 to be dosed \geq 1-week after Patient 2 received the first dose).

In the 3-patient cohorts (i.e. 3 patients treated at the same dose), if 1 out of 3 patients experience a DLT during the first two treatment cycles, the dose cohort will be expanded up to 6 patients. If \geq 2 out of 6 patients experience DLTs, the MTD has been exceeded, and dose escalation will cease. Up to 3 additional patients will be enrolled at the next lowest dose if only 3 patients were treated at that dose level, to confirm safety of that dose. If a DLT is observed already with the first patient in Cohort 1, the Safety Review

Committee (Section 8.1.2.8.1) may suggest and approve a dose de-escalation cohort with at least 50 % reduction of HS-110 and HS-130 (dose level -1).

Once all patients in a cohort have completed the first two cycles of dosing and received at least 2 doses of HS-130/HS-110, the safety and tolerability of the combination treatment administered will be reviewed by the safety review committee (SRC). If 0 out of 3 patients or 1 out of 6 patients experience a DLT, then the SRC may recommend enrollment at the next higher dose level.

Any patient who does not receive two doses of the study treatment during the DLT window of observation (first 2 cycles/4 weeks), for reasons other than study drug-related toxicity and did not experience a DLT will not be taken into account in the assessment of the overall DLT rate for the particular dose level cohort and will be replaced.

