6.2 Dose Interruptions/Withholding

Study drug may be withheld from a patient based on the Investigator's decision in the event of intercurrent illness, adverse event, administrative reasons, or other reasons. If the patient's condition subsequently improves, or the situation that resulted in withholding study drug rectifies itself, the Investigator may resume dosing as soon as possible, unless the delay is more than 2-weeks. Doses should not be skipped.

Dosing should be delayed for any DLT-equivalent toxicity and possible >Grade 2 adverse events considered related to study medication. At the Investigator's discretion, dosing may recommence when the toxicity has resolved to Grade 2 or less. Immune related reactions or allergy should resolve to Grade 1 or less.

Treatment will be discontinued if the next cycle cannot be initiated if a TEAE has not resolved (to acceptable grade) after ≤ 2 weeks.

Patients who miss a dose during Cycle 1 and Cycle 2 may be replaced in the study per Section 5.4.2. The interruption and/or missed dose(s) should be recorded.

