7.3.2.1 Cycle 2 Day 1 ± 2 days (Week 3)

- Physical Exam
- Weight
- Vital signs (blood pressure, heart rate, respiratory rate, and temperature: Before HS130/HS110 treatment; after HS130/HS110 treatment at 30 mins (±5m), and 1hr (±5m))
- ECG in triplicate (a standard 12-lead ECG is taken while patient is in a semi-recumbent position; pre-dose)
- ECOG Performance status ([APPENDIX I](#))
- Blood draw for Hematology
- Blood draw for Blood chemistry tests
- Blood draw for immune response labs (Immunological Effect/immune re-activation) (Pre-dose)
- Blood draw for Cytokines/Chemokines (Pre-dose, and 2 hr ± 10 minutes after completion of HS130/HS110 treatment)
- Record Concomitant medications
- Record Adverse events
- HS-130/HS-110 administration

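### No haematology or chemistry sample is scheduled between dose 1 and the dose 2 visit, so the first-cycle trigger for reverting to 3+3 has no scheduled blood-count, liver or renal data

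*Combined protocol and SAP*

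**What the plan says.** Section 6.1.1 and the synopsis run the first four dose levels in single patients. If a drug-related Grade 2 or higher "event occurs during the first cycle of treatment, the study will revert to 3+3 design starting at that dose level". A Grade 2 injection site reaction with pain is exempt. The notes to Table 3 state: "Each cycle is 14 days".

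Table 3 and Section 7.3 place the safety laboratory panels as follows:

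- **Cycle 1 Day 1 (7.3.1.1):** "Blood draw for Hematology (may be done within 3 days prior", with the same allowance for chemistry.
- **Cycle 1 Day 8 (7.3.1.2):** the only blood item is "Blood draw for immune response labs (Immunological Effect/Immune re-activation".
- **Cycle 2 Day 1 (7.3.2.1):** "Blood draw for Hematology" and "Blood draw for Blood chemistry tests", neither with a stated time relative to dose 2.

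Section 6.2 gives the rule for holding a dose: "Dosing should be delayed for any DLT-equivalent toxicity and possible >Grade 2 adverse events considered related to study medication". It names no laboratory result that must be seen first.

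**The concern.** Section 8.1.2.1 bases the identification of adverse events partly on laboratory results, and haematological toxicity is the first item in the DLT definition (Section 6.1.2). The reversion trigger is evidently meant to respond to such events. The schedule supplies no haematology or chemistry inside the trigger's window.

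This matters more than usual here. HS-130 has not been given to humans, and no formal GLP toxicology study has been done (Sections 2.3.2 and 2.4). Each run-in level needs only one patient, so an event missed in that patient cannot be seen in a second patient at the same level. The minimum stagger between run-in patients is 1 week, about half the time to the first post-dose haematology or chemistry sample.

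**Working it through.** No sample size or error rate is involved. The check is a count on the visit calendar, followed by a comparison of the timing labels.

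**Inputs.** Cycle length is 14 days and visit windows are ±2 days (Table 3). Nominal days are C1D1 = 1, C1D8 = 8 and C2D1 = 1 + 14 = 15. As a check on the numbering, 2 × 14 = 28 days, which matches the 4-week DLT window in Section 6.1.1.

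**Count.** The trigger window is Days 1-14. Haematology and chemistry fall on Days 1 and 15, then on Day 1 of later cycles. I take the C1D1 draw as baseline, because it may be done up to 3 days earlier and no post-dose repeat is listed. Scheduled samples on Days 2-14 = **0**, the same at all four single-patient levels.

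**Delay.** Dose 1 to the first post-dose sample: 15 − 1 = **14 days** nominally. With the C2D1 window it is 14 − 2 = 12 to 14 + 2 = 16 days. An early visit could put the draw on Day 13 or 14, but it is still the dose 2 visit.

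**What the trigger does have in Cycle 1 after dose 1:**

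| Item | Timing |
|---|---|
| Vital signs | 30 min and 1 h after dose 1; Day 8 |
| Cytokines/chemokines | "Blood draw for Cytokines/Chemokines (Pre-dose, and 2 hr ± 10 minutes after completion of HS130/HS110 treatment" |
| Physical exam, weight, ECOG | Day 8 |
| Immune response labs | Day 8 |
| Adverse event recording | throughout |
| Haematology, chemistry | none |

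**Timing labels at C2D1 (7.3.2.1).** ECG and immune labs are marked pre-dose. Cytokines and vital signs are timed both before and after dosing. Haematology and chemistry have no label, and nor do physical exam, weight or ECOG. List order does not settle the question. Dosing comes last at C2D1, but at C1D1 it is listed ahead of a draw marked pre-dose.

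**Which events are affected:**

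- Arises after dose 1 and resolves before C2D1 without symptoms: not measured by any scheduled sample.
- Arises after dose 1 and persists to C2D1: measured, but the plan does not say whether it counts as a first-cycle event.
- Grade 1 or 2 and needing no intervention: not recorded as an adverse event (Section 8.1.2.1), so it might not reach the trigger even if sampled.

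**The case against.** The strongest reply is that the trigger is far from blind. A cytokine sample is taken 2 hours after dose 1 and immune labs on Day 8, and Section 9.3 counts cytokines and chemokines among the safety laboratory evaluations. Day 8 has an examination and adverse event recording, and unscheduled tests are not excluded. The Safety Review Committee evaluates data at each dose level and may ask for more patients at that level (Section 8.1.2.8.1). The 4-week DLT window takes in the C2D1 results. HS-110 has been given to over 100 patients without overt toxicity. On this view, sampling intensity is a judgement and the rest is missing wording.

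Much of this stands, and it rules out several stronger statements that a reader might infer:

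- *That Cycle 1 has no post-dose laboratory data at all.* It has two such samples. Neither measures blood counts, liver function or renal function.
- *That an abnormality first seen at C2D1 falls outside the trigger.* No text equates onset with the date of detection. An abnormality in a sample drawn before dose 2 may well have arisen in Cycle 1. The point is undefined.
- *That the plan permits dose 2 without laboratory data.* A draw is scheduled that day and Section 6.2 has a general delay rule. What is missing is an explicit link between them.
- *That single-patient escalation will continue past a level that should have reverted.* That needs a related, symptomless event that the site, the C2D1 sample and the committee all miss. The documents give no basis for a frequency.

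The reply does not answer the core point. A site that follows the schedule exactly collects no haematology or chemistry after dose 1 in the only cycle the trigger looks at. The HS-110 record does not cover HS-130, and the committee can review only what was measured or reported.

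**Conclusion.** The concern holds in this limited form. There are 0 scheduled haematology or chemistry samples after dose 1 within Cycle 1, and the first comes about two weeks later, at the dose 2 visit. The reversion trigger is therefore blind to symptomless laboratory toxicity that resolves before C2D1. Two points are also left open: how a C2D1 finding counts toward the trigger, and whether the C2D1 draws come before dosing and are reviewed before it.

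This rests on nominal visit days, on reading the C1D1 draw as baseline, and on sites drawing no unscheduled samples. It is a modest weakness in a first-in-human safeguard with partial backstops, and it is worth correcting because the correction is cheap.

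**What to change.** 1. Add the existing haematology and chemistry panels to the Cycle 1 Day 8 visit in Table 3 and Section 7.3.1.2.
2. In Table 3 and Section 7.3.2.1, state when the Cycle 2 Day 1 haematology and chemistry draws are taken relative to dosing, as is already done for ECG, immune labs and cytokines at that visit.
3. Reconcile the trigger window (Section 6.1.1 and synopsis), the laboratory schedule (Table 3 and Section 7.3) and the dose-delay rule (Section 6.2), including how findings at Cycle 2 Day 1 are treated. The content of those rules is for the sponsor and investigators to settle.

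Cost: about 5 + 5 = 10 mL more blood per patient, raising the Day 8 draw from about 23 to about 33 mL. It uses an existing visit and venepuncture and needs a few wording changes. The chance of reverting to 3+3 rises slightly. The gain is mainly for Grade 3 or higher abnormalities and Grade 2 ones needing intervention, because of the recording exclusion in Section 8.1.2.1.

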7.3.2.1 Cycle 2 Day 1 ± 2 days (Week 3)

- Physical Exam
- Weight
- Vital signs (blood pressure, heart rate, respiratory rate, and temperature: Before HS130/HS110 treatment; after HS130/HS110 treatment at 30 mins (±5m), and 1hr (±5m))
- ECG in triplicate (a standard 12-lead ECG is taken while patient is in a semi-recumbent position; pre-dose)
- ECOG Performance status ([APPENDIX I](#))
- Blood draw for Hematology
- Blood draw for Blood chemistry tests
- Blood draw for immune response labs (Immunological Effect/immune re-activation) (Pre-dose)
- Blood draw for Cytokines/Chemokines (Pre-dose, and 2 hr ± 10 minutes after completion of HS130/HS110 treatment)
- Record Concomitant medications
- Record Adverse events
- HS-130/HS-110 administration

7.3.2.2 Cycle 2 Day 8 ± 2 days (Week 4)

- Physical Exam
- Weight
- Vital signs (blood pressure, heart rate, respiratory rate, and temperature)
- ECOG Performance status ([APPENDIX I](#))
- Blood draw for immune response labs (Immunological Effect/Immune re-activation)
- Record Concomitant medications
- Record Adverse events

7.3.3 Cycle 3 and Beyond (Day 1± 2 days)

- Physical Exam
- Weight
- Vital signs (blood pressure, heart rate, respiratory rate, and temperature only before HS130/HS110 treatment)
- ECG in triplicate (a standard 12-lead ECG is taken while patient is in a semi-recumbent position) (pre-dose)
- ECOG Performance status ([APPENDIX I](#))
- Blood draw for Hematology

- Blood draw for Blood chemistry tests
- Blood draw for Cytokines/Chemokines (Only if patient is symptomatic)
- Record Concomitant medications
- Record Adverse events
- HS-130/HS-110 administration
- On-treatment Biopsy (within 5-14 days after patient completes 2nd dose of HS-130/HS-110). Note that coagulation tests should be reviewed prior to procedure per institutional standards.
- Imaging for tumor measurements by RECIST 1.1¹ (every 8-weeks \pm 1 week from C1D1 until disease progression)

7.4 30-Day Safety Follow up Visit from Last Dose (\pm 3 days)

The following assessments will be performed at 30 days \pm 3 days of the last treatment for all patients who have discontinued treatment with HS-130/HS-110:

- Physical Exam
- Weight
- Vital signs (blood pressure, heart rate, respiratory rate, and temperature)
- ECG in triplicate (a standard 12-lead ECG is taken while patient is in a semi-recumbent position)
- ECOG Performance status ([APPENDIX I](#))
- Blood draw for Hematology
- Blood draw for Blood chemistry tests
- Blood draw for immune response labs (Immunological Effect/Immune re-activation)
- Record Concomitant medications
- Record Adverse events

7.5 Post-treatment Follow-up (\pm 1 week)

The following assessments will be performed every 12-weeks starting from the date of last dose for any patient that stops treatment for any reason other than progressive disease until disease progression or if the patient starts a new treatment. Any AEs deemed related to study drug will also be recorded.

- Record concomitant medications and/or treatments
- Record Adverse events
- Imaging for tumor measurements (CT scan or MRI)

